3.2 DRUG ADMINISTRATION

Radiation delivery is described in Section [3.8](#).

Patients will be instructed to maintain good hydration for the 24 hours prior to the 18F-DCFPyL PET/CT (recommended 1-2 liters of fluid, unless medically contraindicated). Patients will report to the NCI Molecular Imaging Clinic on the day of their 18F-DCFPyL PET/CT imaging sessions and peripheral venous access will be obtained. Patency of the venous access will be demonstrated with a saline flush and the patient will then receive 6-6.5 mCi of 18F-DCFPyL as an IV bolus (dosing may be modified per Molecular Imaging Branch procedures). A static whole body PET/CT will be performed as part of the 18F-DCFPyL study approximately 2-hours post - injection. In the event that the MIC is unable to accommodate the scan due to machine down time or other unexpected emergency, the scan may be performed in the PET department if the available MIC AI is in agreement. Every attempt will be made to have all scans completed in the same facility for each patient.

3.3 DOSE MODIFICATIONS

There will be no radiation dose modifications.

Due to potential unpredictable delays and the short half-life of 18F, the total dose of 18F-DCFPyL administered may be reasonably reduced at the discretion of the principal investigator or her designee. The lowest acceptable limit for dosing will be 5mCi with increased scan time of 4 minutes per bed, anything lower than this activity will not be injected.

3.4 QUESTIONNAIRES

The following measures/questionnaires will be collected on this trial via paper or electronically. The timing of collection is noted on the study calendar in Section [3.6](#). The total time anticipated to complete all questionnaires below is 20 minutes.

- The Expanded Prostate Cancer Index Composite (EPIC-26) is a prostate cancer health-related quality of life (HQOL) patient self-administered instrument that measures urinary, bowel, sexual, and hormonal symptoms related to radiotherapy and hormonal therapy. The EPIC-26 was developed from the 50-item EPIC questionnaire and was validated using question responses from 252 subjects who had undergone brachytherapy, external beam radiotherapy, or prostatectomy for prostate cancer. A high correlation was observed between the EPIC-50 and EPIC-26 versions for the urinary incontinence, urinary irritation/obstruction, bowel, sexual, and vitality/hormonal domain scores (all $r \geq 0.96$). The correlations between the different domains were low, confirming that EPIC-26 retained the ability to discern the distinct HQOL domains. The internal consistency and test-retest reliability for EPIC-26 (Cronbach's alpha ≥ 0.70 and $r \geq 0.69$, respectively for all HQOL domains) supported its validity. EPIC-26 has been used in multiple RTOG protocols and phase II publications for hypofractionated radiotherapy to the prostate.
- Sexual Health Inventory for Men (SHIM) is a prostate specific questionnaire for assessment of erectile dysfunction. Initially derived from the IIEF, a shortened version to six questions the IIEF-6 or SHIM was created for increased usability in the clinic.
- American Urologic Association Symptom Index Score (AUA-SI) has been established as a measure of radiation morbidity in patients treated for prostate cancer with respect to urinary function and is used routinely as the basis for treatment decisions. Moderate agreement was observed between EPIC domains and the American Urological Association Symptom Index (AUA-SI), providing criterion validity without excessive overlap.
- PROMIS – Depression SF4a: The PROMIS Depression item bank assesses self-reported negative mood (sadness, guilt), views of self (self-criticism, worthlessness), and social cognition (loneliness, interpersonal alienation), as well as decreased positive affect and engagement (loss of interest, meaning, and purpose). The depression short forms are universal rather than disease-specific. All assess depression over the past seven days. PROMIS instruments are scored using item-level calibrations.
- PROMIS – Anxiety SF4a: The PROMIS Anxiety item banks assess self-reported fear (fearfulness, panic), anxious misery (worry, dread), hyperarousal (tension, nervousness, restlessness), and somatic symptoms related to arousal (racing heart, dizziness). Anxiety is best differentiated by symptoms that reflect autonomic arousal and experience of threat. Only one behavioral avoidance item is included in the adult item bank; therefore, behavioral fear avoidance is not fully evaluated. The anxiety measures are universal rather than disease-specific. All assess anxiety over the past seven days.

- PROMIS – Psychosocial Impact Positive SF 4a assess positive psychosocial (emotional and social) outcomes of illness, previously conceptualized in various ways including post-traumatic growth, benefit-finding, and meaning making. Positive Illness Impact refers to positive psychosocial outcomes of illness that can occur as a result of confrontation with one's mortality, such as greater life appreciation, interpersonal relationships and personal resources.
- Decision Regret Scale (DRS) is a 5-item scale measuring distress or remorse after a health case decision. It has been psychometrically validated in the prostate cancer population. The score correlated with satisfaction with the decision ($r=-0.40$ to -0.60), decisional conflict ($r=0.31$ to 0.52), and overall rated quality of life ($r=-0.25$ to -0.27).

Once data is abstracted, questionnaires will be maintained in the research chart (print or electronic). If stored, electronically, these files will have restricted access and be accessible only to members of the study team. In the event that questionnaires are stored electronically, paper copies will be shredded.

3.5 MONITORING DURING STUDY

Six months following treatment, patients in both arms will undergo repeat 18F-DCFPyL imaging only if pretreatment imaging was informative. Serial PSA and serial correlative studies will be collected for two years post-treatment.

3.6 STUDY CALENDAR

| Procedure | Screening/ Baseline | Active SBRT treatment | Post Therapy Follow-up (1, 3 mos) 15 | Post Therapy Follow-up 6 months post-SBRT | Post Therapy Follow-up (9 mos and q 3 mos until 24 mos) 8 | |
|--|------------------------|-----------------------------|---|--|---|--|
| History and PE | X | | | | | |
| Vital signs 10 | X | | X | X | X | |
| Performance Score | X | | | | | |
| Weight | X | | | | | |
| Labs | | | | | | |
| CBC, Acute care panel, LFTs, Testosterone, PT/PTT, Viral serologies 2 | X | | | | | |
| PSA 4 | X | | X 11 | X 11 | X 11 | |
| Biopsies (ultrasound guided)/fiducials 5 | X | | | | | |
| mpMRI 3 | X 3 | | | X 12 | | |
| 18F-DCFPyL PET/CT imaging | X 7 | | | X 6, 12 | | |
| 18F-NaF PET/CT imaging 3 | X | | | | | |
| Whole body bone scan 3 | X | | | | | |
| Clinical evaluation | | X | X 9 | X 9 | X 9 | |
| Adverse Events | X | | Monitored continuously | | | |
| Concomitant Medications | X | | Monitored continuously | | | |
| Correlatives | | | | | | |
| Research Biopsy 5 | X | | | | | |
| Blood 12 | X | X 1 | X | X | X | |
| Urine 12 | X | | X | X | X | |
| Questionnaires | | | | | | |
| EPIC-26, SHIM, AUA-SI, DRS, PROMIS 13, 14 | X | | X | X | X | |

1. Correlative blood sampling should be performed within 24 hours after the last dose of irradiation.
2. CBC with differential, chemistries (to include creatinine BUN, PSA, testosterone, Alk Phos, ALT, AST, Bilirubin), PT, PTT within 4 weeks of study entry. Viral serologies: HIV, Hepatitis B, and Hepatitis C screening within 4 weeks of study entry. Acute Care Panel: (Sodium (NA), Potassium (K), Chloride (CL) Total CO₂ (Bicarbonate), Creatinine, Glucose, Urea nitrogen, eGFR).
3. Whole body bone scan, F18 NaF PET, and multiparametric MRI of the prostate. In selected patients, a CT of the abdomen and pelvis (with oral and IV contrast) may also be obtained for staging, particularly if MRI is not felt to adequately have staged the pelvic and abdominal lymph nodes. All imaging studies should be completed within 3 months prior to study entry. MRI of the prostate obtained more than 3 months (no greater than 5 months prior to entry) may be used if a biopsy has recently been performed, as post-biopsy MRI may not be easily interpretable due to hemorrhage.
4. PSA failure after definitive radiation as defined by the Phoenix criteria (PSA elevation at least 2 ng/dL above post-radiotherapy nadir). Serial PSA and serial correlative studies will be collected for two years post-treatment.
5. Post-Imaging research and diagnostic biopsies of areas in the prostate identified as suspicious and systematic biopsy. If recent systematic biopsies were obtained (within 5 months) systematic biopsies may not be repeated. Fiducial markers to guide radiation treatment will be implanted simultaneously. If biopsy tissue was obtained within 5 months on another protocol and is available for transfer, biopsy will not be repeated unless clinically indicated. Fiducials will not be implanted again if previously placed and visible.
6. Six months following treatment, patients in both arms will undergo repeat 18F-DCFPyL imaging only if pretreatment imaging was informative.
7. If an 18F-DCFPyL study was performed within 4 months prior to enrollment on a different protocol, it will not be repeated at baseline. In patients treated with androgen deprivation therapy that was initiated within 4 months of a DCFPyL obtained on another protocol, this DCFPyL scan may be used as the baseline scan if the patient remains on ADT and the scan was obtained within 12 months of enrollment.
8. +/- 2 weeks at and after 6 month time point.
9. May be completed by remote visit with a member of the study team (e.g., if the patient is not able to return to the NIH CC). Remote visits will be conducted in compliance with NIH, FDA regulations and local policy. A patient may be referred to their local provider or asked to come to the NIH CC for an in-person assessment, if clinically indicated, and at the discretion of the PI. In the case of any visits with participants' local providers, records will be obtained.
10. Vital signs may be omitted during follow up visits if a patient is unable to return at the NIH clinical center and if the clinical evaluation does not indicate a need for collection.
11. As PSA is a standardized test and the results are comparable across laboratories, if the patient is not able to return to the NIH Clinical center, PSA may be obtained locally. If biochemical failure (PSA elevation at least 2 ng/dL above post-radiotherapy nadir) is identified, the second measurement will be obtained for confirmation per **6.3.2**, ideally at the NIH Clinical Center.
12. In the event that the patient is unable to return to the NIH Clinical Center during a follow up visit, imaging may be delayed, but will be completed as soon as feasible. Collection of research blood or urine will be omitted or collected in a delayed fashion.
13. Questionnaires may be collected electronically or by paper.
14. Questionnaires will be available one week prior to each clinical visit.

15. +/- 1 week 1 and 3 month follow up visits.

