were negative on PET, were in bone and considered indeterminate for malignancy or due to trauma. One true metastatic bone lesion that was PET negative may have been suppressed by antiandrogen therapy. Surprisingly, blood pool activity remained moderately persistent throughout the imaging. Possible explanations include binding to a free form of PSMA circulating in the blood or non-specific protein binding.

The relationship between androgen receptor (AR) and PSMA expression is complex. Evans et al demonstrated that a functional androgen receptor (AR) is required for PSMA expression and AR suppression results in lower expression which can be quantitatively imaged with PET. (34) However, Androgen deprivation therapies, such as MDV3100 can increase ^{64}Cu –antiPSMA J591 uptake. The NIH Molecular Imaging Clinic's (MIC) experience with ^{18}F -DCFBC in metastatic prostate cancer suggests that patients fully suppressed on androgen deprivation therapy (ADT) have low PSMA expression and patients who are manifestly castrate resistant have high PSMA expression. Interestingly, ^{18}F DCFBC scans show a mix of lesions, some suppressed and others expressing PSMA among the various metastases. The NCI Molecular Imaging Clinic/Molecular Imaging Branch (MIB) has imaged 45 patients with localized, recurrent or metastatic disease with ^{18}F -DCFBC. Encouraging observations of localized disease show focal uptake in tumor and not in benign hyperplasia ([Figure 1](#)).

[figure not shown]

Figure 1. Localized prostate cancer images in patient with high risk cancer (A) Axial ^{18}F -DCFBC PET demonstrating focal uptake in tumor but not in benign prostatic hyperplasia. (B) Corresponding MR image showing malignant and benign lesions. (C) Axial ^{18}F -DCFBC PET and CT fusion image.

[name] group at Johns Hopkins University developed a second-generation low molecular weight, PSMA targeted radiotracer, 2-(3-(1-carboxy-5-[(6-[^{18}F] fluoro-pyridine-3-carbonyl)-amino]-pentyl)-ureido)-pentanedioic acid (^{18}F -DCFPyL). This compound is similar to the first-

generation molecule but with enhanced features. They found tissue binding affinity to be more than 5 times greater than ¹⁸F DCFBC and with significantly less blood pool activity. Their preclinical studies in prostate cancer mice models revealed a maximum target to muscle background ratio of 400:1 at 120 minutes compared to ¹⁸F DCFBC's ratio of 20:1. (35) They noted comparably favorable pharmacokinetics and dosimetry profile.

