2.4 BASELINE EVALUATION

- Clinical evaluation: clinical assessment with attention to any new medications or interventions since screening history and physical examination (to be completed within 2 weeks of study entry, screening history and physical examination is acceptable if obtained within the 2-week interval)
- Laboratory evaluation: CBC with differential, BUN, Creatinine, Alk Phos, ALT, AST, Total Bilirubin, PSA, Testosterone, PT, PTT, Hepatitis B, and Hepatitis C (within 4 weeks of study entry)
- 18F-DCFPyL imaging (will not be repeated if performed on a different protocol within 4 months prior to study enrollment).
- Post-Imaging research and diagnostic biopsies of areas in the prostate identified as suspicious and systematic biopsy. If recent systematic biopsies were obtained (within 5 months) systematic biopsies will not be repeated. Fiducial markers to guide radiation

treatment will be implanted simultaneously if not previously placed or visible

- Questionnaires (to be completed prior to treatment and within 2 weeks prior to SBRT). See Section [3.4](#) for further details. Expanded Prostate Cancer Index Composite (EPIC-26), SHIM, AUA-SI, PROMIS Depression SF4a, PROMIS Anxiety SF4a, PROMIS Psychological Impact Positive SF 4a, Decision Regret Scale
- Correlative assays (to be completed prior to treatment and within 2 weeks prior to SBRT). See Section [5.1](#) for further details. Collection of Plasma – three 8 cc EDTA), urine (15cc in a sterile cup), and research biopsies. In patients with active Hepatitis B or C, some research blood work may not be drawn.

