10.3 POPULATIONS FOR ANALYSES

All enrolled patients that initiate treatment with SBRT will be considered evaluable for toxicity. Patients that complete at least one post-treatment PSA will be considered evaluable for biochemical control and biochemical relapse free survival. Patients that complete QoL measures at 3 months will be considered evaluable for these measures. Patients undergoing biopsy following DCFPyL studies will be considered evaluable for the sensitivity and positive predictive value of this study regardless of whether treatment is received.

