10.4.3 Analysis of the Secondary Endpoints

- Define the dose-limiting toxicities and toxicity profile of image-guided, focally dose escalated prostate SBRT in patients previously treated with radiotherapy: DLTs will be reported descriptively.
- Describe the rate of PSA control (bPFS, PSA < 2 ng/dL above post SBRT nadir) at 1 and 2 years after treatment with focally dose escalated SBRT for locally recurrent prostate cancer after irradiation: bPFS will be estimated by the Kaplan-Meier survival analysis and effects of clinical variables on bPFS will be assessed by the Cox proportional hazards model.
- Describe the effects of focally dose escalated prostate SBRT on patient reported outcomes (SHIM, AUA Symptom Index, EPIC-26) in patients previously treated with radiotherapy. The quality of life scores will be summarized at baseline and for each visit. Linear mixed effects model will be used to model quality of life scores at baseline and during and after treatment in which random intercept and random slope are used to account for patient-specific trajectory of quality of life scores. Changes of quality of life scores during and after treatment will be calculated from the estimated linear mixed effect model.
- Evaluate 18F-DCFPyL imaging as a method to detect locally recurrent prostate cancer after radiation. The sensitivity and specificity of DCFPyL for detecting locally recurrent prostate cancer (at baseline) will be reported using biopsy as the gold standard.

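### The 18F-DCFPyL accuracy analysis pools older scans followed by ADT, and scans taken on ADT, so treatment and elapsed time can be counted as scan errors

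*Combined protocol and SAP*

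**What the plan says.** Evaluating 18F-DCFPyL for local recurrence is a secondary objective (section 1.1.2). Section 10.1 hypothesises high sensitivity and positive predictive value (PPV) and gives no numeric target. Section 10.4.3 sets the analysis: "The sensitivity and specificity of DCFPyL for detecting locally recurrent prostate cancer (at baseline) will be reported using biopsy as the gold standard". Section 10.3 sets the population: "Patients undergoing biopsy following DCFPyL studies will be considered evaluable for the sensitivity and positive predictive value of this study". Neither section mentions ADT, sets a maximum interval, or says which biopsy is the reference when there is more than one.

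Three provisions decide which scans enter:

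- Section 2.4: "18F-DCFPyL imaging (will not be repeated if performed on a different protocol within 4 months prior to study enrollment". It gives no exception.
- Section 3.6, footnote 7, repeats that rule ("If an 18F-DCFPyL study was performed within 4 months prior to enrollment on a different protocol, it will not be repeated at baseline") and then makes an exception for "androgen deprivation therapy that was initiated within 4 months of a DCFPyL obtained on another protocol". For these men the footnote provides: "this DCFPyL scan may be used as the baseline scan if the patient remains on ADT and the scan was obtained within 12 months", counted back from enrollment. It does not say whether ADT began before or after the scan.
- Section 4 discourages concurrent ADT but allows it, and section 2.1.2 does not exclude it, so a newly obtained baseline scan can also be taken on ADT.

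For biopsies, section 2.4 and footnote 5 allow reuse up to 5 months. Section 3.7 uses 4 months for the standard comprehensive biopsies.

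The protocol recognises elsewhere that ADT matters. Section 1.2.2 reports clinic experience that "patients fully suppressed on androgen deprivation therapy (ADT) have low PSMA expression". Section 6.3.3 holds ADT-treated men out of the biochemical progression-free survival (bPFS) endpoint until testosterone recovers. There is no corresponding rule for imaging accuracy.

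**The concern.** An accuracy estimate assumes that the scan and the reference biopsy describe the same disease. Two situations permitted here strain that assumption, and they differ in kind.

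First, a scan taken off ADT may be paired with a biopsy taken many months later under ADT. A lesion correctly seen on the scan could then be negative or unevaluable at biopsy and be counted as a false positive. New growth over the interval could be counted as a false negative. Neither is a fault of the scan.

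Second, a scan taken on ADT may be paired with a biopsy at about the same time. A missed lesion is then a genuine miss, but one that describes the tracer under suppression. Pooled with off-ADT scans, it makes the overall figure depend on how many men happened to be on ADT.

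At stake is the interpretation of the sensitivity, specificity and PPV reported for this objective. A reader could not tell how far they describe the tracer and how far the case mix and timing.

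**Working it through.** The plan gives no sample size, precision or target for this endpoint, so there is no figure to reproduce. The check has three parts.

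**1. Time and ADT exposure between scan and biopsy**

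Inputs: oldest reusable scan, 12 months before enrollment (footnote 7); ADT start within 4 months of the scan (footnote 7); biopsy reuse window, 5 months (section 2.4, footnote 5) or 4 months (section 3.7). I assume that the biopsy windows count back from enrollment.

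Let b be months from biopsy to enrollment, and s the months from scan to ADT start (negative if ADT came first).

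Gap = 12 − b. ADT exposure at biopsy = 12 − s − b.

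| Biopsy timing | Gap from a 12-month-old scan | ADT if started 4 months after scan (s = 4) | ADT if started 4 months before scan (s = −4) |
|---|---|---|---|
| b = 5 | 7 months | 3 months | 11 months |
| b = 4 | 8 months | 4 months | 12 months |
| b = 0 (enrollment) | 12 months | 8 months | 16 months |

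A biopsy after enrollment adds to every entry. The 8-month minimum therefore holds at enrollment. With a reused biopsy the minimum is 3 months.

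**2. Possible effect on the estimates (all inputs assumed)**

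Sensitivity: let S be sensitivity in unaffected scans, f the share of affected scans and d the loss in them. Apparent sensitivity = S − f·d. With S = 0.90:

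- f = 0.1, d = 0.1: 0.90 − 0.01 = 0.89
- f = 0.2, d = 0.3: 0.90 − 0.06 = 0.84
- f = 0.4, d = 0.4: 0.90 − 0.16 = 0.74

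If ADT raised the signal, d would be negative and the figure would move up: f = 0.4, d = −0.1 gives 0.90 + 0.04 = 0.94.

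PPV, at lesion level: let f be the share of scan-positive lesions in mismatched pairs and c the share of true scan-positive lesions in those pairs that are biopsy-negative after ADT. Apparent PPV = 0.90 × (1 − f·c).

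- f = 0.2, c = 0.2: 0.90 × 0.96 = 0.86
- f = 0.3, c = 0.4: 0.90 × 0.88 = 0.79

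**3. Precision cost of a smaller main set**

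Exact (Clopper–Pearson) 95% intervals at an observed sensitivity of about 0.90, starting from the maximum of 42 evaluable patients in section 10.2:

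| Detected / total | 95% interval |
|---|---|
| 38/42 | 0.774–0.973 |
| 31/34 | 0.763–0.981 |
| 27/30 | 0.735–0.979 |
| 22/25 | 0.688–0.975 |

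The number that would leave the main set is not in the documents.

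**The case against.** **The exception may rarely be used.** Footnote 7 is permissive, applies only to men who stay on ADT, and section 4 discourages ADT. This stands: a reader might infer that scan errors are being created, but the documents show only that they can be. The analysis set should still deal with pairs that the protocol expressly admits.

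**The direction is not established.** Section 1.2.2 calls the relation between androgen receptor and PSMA complex. It reports that therapy such as MDV3100 can raise uptake of a PSMA agent, and that castrate-resistant patients have high expression. Its low-expression remark concerns a different tracer, 18F-DCFBC, in metastatic disease. This stands: a reader might infer a one-way loss of sensitivity, and the documents do not support that. It is also a reason to report the groups separately, because a pooled figure cannot be corrected afterwards.

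**Eligibility limits the PPV problem.** Section 2.1.1.1 requires histological confirmation of local recurrence, so a scan-positive man can hardly be free of disease. This stands at patient level. Section 3.1 has lesions seen on imaging biopsied so that imaging can be compared with pathology, and agreement by lesion remains exposed.

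**The effect is small against the noise.** Of the sensitivity losses illustrated with f and d each from 0.1 to 0.4, only the most extreme (0.74) falls outside the 38/42 interval of 0.774–0.973. The endpoint is descriptive, with no test or decision rule. This stands and limits the importance of the point, but a wide interval does not make a mixed estimate interpretable.

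**Off-ADT scans alone would answer a different question.** The enrolled population includes men on ADT. This is fair, and the fix reports by ADT status and does not discard on-ADT scans.

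**Conclusion.** The gap is real. Footnote 7 admits scans up to 12 months before enrollment in men who began ADT around the scan and remain on it, section 4 admits scans taken on ADT, and sections 10.3 and 10.4.3 pool them all against biopsy. Treatment and elapsed time can therefore be scored as false positives or false negatives.

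The timing follows from the stated windows: for the oldest permitted scan, at least 7 months to a reused biopsy and 12 months or more to one at or after enrollment. The effect on accuracy cannot be sized from the documents. The figures of 0.89 to 0.74 for sensitivity and 0.86 to 0.79 for lesion-level PPV rest wholly on assumed shares and losses, and the net direction is open.

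Two further inferences should be resisted. The 4 months in section 2.4 run from scan to enrollment and are not a scan-to-biopsy limit. Section 2.4 and footnote 7 do not set rival general rules: footnote 7 restates the 4-month rule and adds an exception that section 2.4 omits. The point concerns a descriptive secondary endpoint and leaves the MTD determination untouched.

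**What to change.** In sections 10.3 and 10.4.3:

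1. Exclude from the main accuracy estimate the pairs that use footnote 7's 12-month exception, and those in which ADT was started between the scan and the reference biopsy.
2. Report sensitivity, specificity and PPV separately for scans taken on and off ADT, and state whether the unit is the patient or the lesion.
3. Give the estimate from all pairs as a sensitivity analysis.
4. Name the reference biopsy and set a scan-to-biopsy limit. The limit must allow for a scan 4 months before enrollment plus the time from enrollment to biopsy, so that compliant off-ADT pairs are not dropped.

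Bring section 2.4 and footnote 7 into agreement, for example by carrying the exception into section 2.4 if it is meant to stand. The 5-month and 4-month biopsy reuse windows also need reconciling.

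The cost is a somewhat smaller main set and wider intervals: going from 38/42 to 27/30, for example, moves the 95% interval from 0.774–0.973 to 0.735–0.979. Section 6.1.1 already captures ADT use and testosterone. It does not expressly list scan, biopsy or ADT start dates, so these may have to be retrieved for scans done on other protocols. No patient's treatment or imaging changes.
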